
2. Objectives (include all primary and secondary objectives)

Primary objectives:

- 1) To determine to what extent pathological abnormalities (i.e., MT measures of demyelination, and DTI measures of axonal integrity) are associated with sensory and motor impairments and locomotor patterns (i.e., kinematic walking measures and quantitative motor impairments) in women with AMN.
- 2) To determine the extent to which tract specific anatomy (demyelination, axonal loss) predict who will respond best to three months of progressive resistance training (PRT) in female carriers.

Date: July 1, 2013
Principal Investigator: [name]
Application Number: NA_00045673

3. Background (briefly describe pre-clinical and clinical data, current experience with procedures, drug or device, and any other relevant information to justify the research)

Adrenomyeloneuropathy (AMN) is the adult phenotype of X-linked adrenoleukodystrophy (X-ALD), a progressive disorder that affects the nervous system, adrenal cortex and testes due to a defect in the gene ABCD1, which has been mapped to Xq28. Adult onset of symptoms of disease not only occurs in 60% of males with the X-ALD mutation in their most productive years of life but also 50% of female carriers, though often a decade later than that of the men. Diagnosis and treatment studies for AMN have principally focused on men despite the prevalence of symptoms in female carriers. AMN is characterized by progressive non-inflammatory axonopathy in the corticospinal (CST) and Dorsal Column-Medial Lemniscal (DC-ML) tracts of the brain and spinal cord. There is additional evidence of demyelination caused by secondary inflammatory mechanisms. AMN including women carriers have been characterized as having primarily lower extremity spasticity, with abnormalities in vibration sensation, strength, walking, and balance that progress during 5 to 20 years in a variable pattern. Our preliminary data show that women carriers can have symptoms that are as severe as the men. There are currently no medical treatment options available for women carriers; these patients have dismal hopes for improvement, except with rehabilitation. There is a glaring need for more knowledge and more effective rehabilitative treatment approaches for women ALD carriers.

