Healthy controls have the same exclusion criteria as women with AMN with 2 exceptions, (1) they can be age 21-70 years, and (2) they will not be carriers for X-ALD. They must have normal neurological function.

6. Drugs/ Substances/ Devices

- a. The rationale for choosing the drug and dose or for choosing the device to be used.

N/A

- b. Justification and safety information if FDA approved drugs will be administered for non-FDA approved indications or if doses or routes of administration or participant populations are changed.

N/A

- c. Justification and safety information if non-FDA approved drugs without an IND will be administered.

N/A

Study Statistics

- a. Primary outcome variable.

Primary outcome variables for sensorimotor impairments include: vibration sensation, strength (average values from the hip and ankle muscles, both flexion and extension, will be used), and spasticity from the ankle flexor/extensor muscles bilaterally.

The primary variables of interest for white matter integrity in this analysis will be fractional anisotropy (FA) and magnetization transfer ratio (MTR).

Other primary outcome variables include correlations to determine relationships between sensorimotor impairments and between white matter integrity variables in the tracts of interest. Multiple regression analysis we will also be used determine to what extent sensorimotor impairments are related to white matter integrity variables.

The primary outcome variable for the exercise intervention we will calculate a functional composite score (FS) for each person that will incorporate 4 tests that functionally challenge the lower extremity: 1) sit to stand, 2) Up and Go test, 3) 25-foot timed walk, and 4) 6-minute walk test.

- b. Secondary outcome variables.

To determine response to three months of the exercise intervention:

1. We will calculate pre- to post- trial differences between groups using an unpaired t test. Changes between pre- and post-trial within groups will also be compared with paired t tests.

Date: July 1, 2013
Principal Investigator: [name]
Application Number: NA_00045673

2. To determine change in hip flexion, FS from post- to follow up session within groups will be compared with paired t tests. [(Exercise_{followup}-Exercise_{post}) vs (Exercise_{post}-Exercise_{pre})], will be evaluated.

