 3. To evaluate possible time and group interactions during the intervention within groups we will use multivariate ANOVA's. Significant interactions will be evaluated with a mixed effects linear regression.
 4. To determine change in EDSS scores over each session we will use with Wilcoxon signed rank test.
 5. To determine whether specific changes in the primary outcome measures are predicted by the changes in tract specific demyelination and axonal loss (i.e., MTR and FA) we will determine how much each impairment changed from the pre- to post- session.
 6. We will conduct separate correlations to determine the relationship between the primary outcomes, and extent of demyelination and axonal loss pre- and post-intervention.
 7. Multiple regression analyses will also be used to determine which pattern of white matter damage (i.e., demyelination, axonal loss) best predicts hip flexion and FS.
- c. Statistical plan including sample size justification and interim data analysis.

Preliminary studies of heterozygote data from our laboratory suggest that a minimum of 12 subjects are needed to obtain adequate statistical power. Hip flexion strength data from female carriers are: 11.2 ± 4.6 kg. Using these values, differences between groups on the order of one SD will be statistically significant with a power of 0.8 given a sample size of 12 subjects. To account for attrition, we have added 25% to this total. Therefore, our initial plan is to have 15 female carriers for this project and 15 healthy controls. All power calculations assume two-tailed tests with $\alpha = 0.05$. Analysis will be done using Statistica software (StatSoft Inc., Tulsa OK) or Stata (StataCorp).

- d. Early stopping rules.

None.

7. Risks

- a. Medical risks, listing all procedures, their major and minor risks and expected frequency.

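### The 80% power claimed for a one-SD group difference with 12 subjects does not follow from the plan's inputs: 12 per group gives about 65%, and 15 per group about 75%.

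*Combined protocol and SAP*

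**What the plan says.** The only sample size justification is in Study Statistics, part c. It gives hip flexion strength in female carriers as 11.2 ± 4.6 kg, calls 12 subjects the minimum for adequate power, and states that "differences between groups on the order of one SD will be statistically significant with a power of 0.8 given a sample size of 12" subjects. It adds 25% for attrition, giving 15 carriers and 15 healthy controls. On sidedness it says "All power calculations assume two-tailed tests", with alpha 0.05.

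The between-group test is named in Study Statistics, part b, item 1: "We will calculate pre- to post- trial differences between groups using an unpaired t test".

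The two primary objectives (section 2) are of another kind. The first asks how far imaging abnormalities "are associated with sensory and motor impairments and locomotor patterns" in women with AMN. The second asks whether tract anatomy predicts which carriers respond to training.

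**The concern.** A two-sided comparison of two independent groups at one SD usually needs about 16 or 17 per group for 80% power, so 12 looks too few. Since the enrolment of 15 plus 15 comes directly from the figure of 12, an error there carries through to the whole sample size.

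The stakes are in how results are read. Someone who believes the study has 80% power will take a non-significant group difference as fairly good evidence against a one-SD effect, which it is not if true power is nearer 65%. The risk is greater for the imaging correlations. They are the study's main purpose, yet the general assurance of adequate power was never worked out for them.

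**Working it through.** **Inputs, all from Study Statistics**
- Standardised difference d = 1.0 (part c: "differences between groups on the order of one SD")
- Two-sided alpha 0.05 and stated power 0.80 (part c)
- n = 12, read as per group because 12 × 1.25 = 15 carriers, with 15 controls (part c)
- Unpaired t test (part b, item 1)
- SD 4.6 kg, from carriers. No control SD is given, so a common SD is assumed. It is needed only to convert to kg.

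**Step 1. Try to reproduce 0.80**

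Power = P(|T| > t₀.₉₇₅), where T is noncentral t with 2n − 2 degrees of freedom and noncentrality d√(n/2).

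| n per group | noncentrality | critical t | power |
|---|---|---|---|
| 6 (12 in total) | 1.732 | 2.228 | 0.347 |
| 12 | 2.449 | 2.074 | 0.649 |
| 15 | 2.739 | 2.048 | 0.753 |
| 16 | 2.828 | 2.042 | 0.781 |
| 17 | 2.915 | 2.037 | 0.807 |

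The normal approximation is more generous but also falls short. At 12 per group it gives Φ(2.449 − 1.960) = Φ(0.489) = 0.688, and at 15 it gives Φ(2.739 − 1.960) = 0.782. Its required size is 2(1.960 + 0.842)² / 1² = 15.7, so 16 per group.

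**Step 2. Look for a reading that yields 12**
- One-sided normal approximation: 2(1.645 + 0.842)² = 12.4 per group, and power at 12 is Φ(2.449 − 1.645) = 0.789. This is the only reading tried that comes within two points of 0.80 without an added input. It contradicts the two-tailed statement. The one-sided t test gives 0.767.
- Paired or one-sample t test with d = 1 on the difference: n = 10 already gives 0.803, and n = 12 gives 0.883.

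**Step 3. What the planned numbers can detect with 80% power**
- 12 per group: 1.20 SD, or 1.197 × 4.6 = 5.5 kg
- 15 per group: 1.06 SD, or 1.06 × 4.6 = 4.9 kg

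**Step 4. The SD and the planned test**

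The 4.6 kg is the spread of strength between women at one time, whereas item 1 compares pre-to-post changes. With the same SD at both times, the SD of change is 4.6√(2(1 − ρ)), where ρ is the pre-post correlation. It equals 4.6 kg only when ρ = 0.5. The plan gives no ρ. Taking a 4.6 kg difference in change with 12 per group, power is 0.649 at ρ = 0.5, 0.745 at 0.6 and 0.856 at 0.7.

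**Step 5. The primary objectives**

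For a single correlation among carriers (Fisher z), the value detectable with 80% power is tanh((1.960 + 0.842)/√(n − 3)).
- n = 12: tanh(2.802/3.000) = 0.73
- n = 15: tanh(2.802/3.464) = 0.67

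For a true r of 0.5, where atanh(0.5) = 0.549:
- n = 12: power Φ(0.549 × 3.000 − 1.960) = 0.38
- n = 15: power Φ(0.549 × 3.464 − 1.960) = 0.48

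**The case against.** The arithmetic at exactly one SD is not in dispute. The case for leniency rests on five points.

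- **Loose wording.** The plan speaks of the order of one SD, and 1.20 SD, where 12 per group does reach 80%, might be called that. But the only effect size written down is one SD, and a power figure has to be judged at the effect it names.
- **The test is not named beside the power sentence.** Section 4a describes the controls as age- and gender-matched. Twelve matched pairs with a within-pair correlation of about 0.36 would give 0.796. So a paired analysis is not ruled out in principle; the paired check in Step 2 covers only a one-SD paired difference. However, the plan states no such correlation and names no matched-pair comparison of the groups.
- **The SD may differ in practice.** The hip flexion entry range in section 5, 6.6 to 15.8 kg, is exactly 11.2 ± 4.6. If every carrier qualified that way and strength were normal before truncation, the carriers' SD would be about 2.5 kg, and simulated power for 4.6 kg (control SD 4.6, 12 per group) would be about 0.83. The alternative entry route through hip extension weakens this, and the control SD is unknown. The point does not rescue the sentence, but it does mean that any kg figure must carry its equal-SD assumption.
- **The shortfall at 15 per group is modest.** It is 75.3% by the t test and 78.2% by the normal approximation. This is correct, but the plan makes its claim for 12, with 15 as the allowance for losses.
- **Limited consequences.** The plan has no stopping rule and makes no numerical power claim for the correlations. How null results will be read is a matter of inference. The SD and correlation remarks are therefore additions to the arithmetic error, not part of it.

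**Conclusion.** The power statement is wrong as written. With a one-SD difference, two-sided 0.05 and an unpaired t test, 12 per group gives 64.9% power (68.8% by the normal approximation). That is 11 to 15 percentage points below the stated 80%, so it is not a rounding matter. Full retention of 15 per group gives 75.3%, and 80% needs 17 completers per group. Reading 12 as the total makes it worse.

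This rests on reading 12 as per group, on independent groups with a common SD, and on taking one SD literally. The alternatives that would reach 80% each need a correlation, an SD or a larger effect that the plan does not state, or a one-sided test that it excludes. Because this sentence is the whole basis for the sample size, it needs correcting even though enrolment need not change.

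**What to change.** Keep 15 plus 15 and replace the power sentence with something like:

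*With 12 completers per group, a two-sided unpaired t test at 0.05 has 65% power for a difference of 1.0 SD in hip flexion strength and 80% power for 1.20 SD (5.5 kg). If all 15 per group complete, power is 75% for 1.0 SD, and 80% for 1.06 SD (4.9 kg). The kg values assume an SD of 4.6 kg in both groups.*

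Then:
- State that 4.6 kg is a cross-sectional SD, so these figures apply to a comparison of strength at one time and not to the comparison of changes.
- Add that the primary association analyses have 80% power only for |r| of about 0.73 with 12 carriers or 0.67 with 15. Report those associations with confidence intervals, and do not take a non-significant result as showing no association.
- If a matched-pair analysis or an unequal-SD calculation was intended, name it and give the correlation or SD used.

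The cost is wording and a less favourable stated figure. No participants are added and no analysis changes, unless a matched-pair analysis was intended.

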Conventional magnetic resonance imaging techniques along with the Loes scale (i.e., categorical rating scale) have been used to evaluate progression of X-ALD disease burden in children with moderate success. Pathologic studies show that dying back of axonal loss is a primary pathogenic mechanism of AMN and much of the permanent disability results from axonal damage. However, attempts at correlating clinical disability with axonal injury have had limited success due to clinical rating scales that do not adequately measure all aspects of the disease, coupled with an inability for routine imaging techniques to depict specific clinically involved fiber tracts in the brain and spinal cord. Our preliminary data show that we can distinguish female carriers from control subjects using novel techniques such as magnetization transfer (MT) imaging. In addition, we have previously shown that damage measured using tract specific MRI, specifically magnetization transfer and diffusion tensor imaging (DTI) correlates with physical impairments in individuals with the degenerative disease of multiple sclerosis.

In conjunction with advanced DTI and MT metrics developed at the Kirby Imaging Center of the Kennedy Krieger Institute, we plan to capitalize on the tools within our motion laboratory, having thorough experience with them in assessing spasticity, ataxia, sensation, and muscle strength in individuals with AMN and in individuals with multiple sclerosis. We predict that MT imaging and DTI, which measure the integrity of white matter and fiber tracts in the brain and spinal cord, will aid in understanding the extent to which axonal/myelin anatomy are associated with sensory and motor impairments as well as locomotor patterns with the goal of understanding how to treat physical disability more effectively.

4. Study Procedures

- a. Study design, including the sequence and timing of study procedures (distinguish research procedures from those that are part of routine care).

Date: July 1, 2013
Principal Investigator: [name]
Application Number: NA_00045673

We will test female heterozygote carriers of X-ALD and healthy age- and gender-matched controls.

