c. Blinding, including justification for blinding or not blinding the trial, if applicable.

All subjects in the study will take part in the exercise intervention. We are unable to blind the subjects or testers to the intervention which has been discussed in other similar studies as a limitation. However, we have specified guidelines that the PT will follow for progression of the exercise program to alleviate bias as much as possible.

d. Justification of why participants will not receive routine care or will have current therapy stopped.

N/A

Date: July 1, 2013
Principal Investigator: [name]
Application Number: NA_00045673

e. Justification for inclusion of a placebo or non-treatment group.

N/A

f. Definition of treatment failure or participant removal criteria.

Patients selected for the study will be removed if they: 1) inform us that they become pregnant during the study, 2) are unable to follow the requirements of the study, or 3) request to be removed.

We are not aware of a particular pregnancy risk, but the inclusion of a subset who are pregnant would be difficult to interpret compared to non-pregnant participants.

g. Description of what happens to participants receiving therapy when study ends or if a participant's participation in the study ends prematurely.

The subject's medical care will continue unaltered when the study ends or if a subject is removed from the study.

5. Inclusion/Exclusion Criteria

Inclusion criteria for women with X-ALD

- confirmed diagnosis, X-ALD heterozygote carrier
- no medical contraindication to participating in a strength training program
- able to follow complex directions as determined by a score of ≤ 1 on a subset of questions taken from the NIH Stroke scale (Brott et al. 1989)
- hip flexion strength: 6.6-15.8kg or hip extension strength: ≤ 18.3 kg
- normal passive range of motion at hips/knees/ankles
- scale of 1-6 on the EDSS
- able to walk ≥ 50 m
- age 21-65

Exclusion criteria

- Evidence of other neurological deficit that could interfere, such as previous stroke or muscle disease
- congestive heart failure
- cancer
- orthopedic conditions
- severe pain that precludes study participation
- seizures
- pregnancy
- other medical condition that precludes participation in an exercise program, e.g., unstable angina, uncontrolled diabetes, uncontrolled hypertension

Date: July 1, 2013
Principal Investigator: [name]
Application Number: NA_00045673

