The potential risks in this study are very low. The study is entirely non-invasive. Subjects may become fatigued or lose their balance during walking or standing and they may have slight muscle soreness, this has occurred very rarely in past studies. There is a potential that subjects may have an allergy/sensitivity to the tape used for marker placement, in this situation we will use a stocking net that we have in the lab to hold the marker in place instead of tape. Subjects may become uncomfortable while in the MRI scanner. Any incidental findings on MRI will be provided to the patient by [name] by phone or if necessary in a clinical visit. If there are new findings the individual will be assisted in obtaining follow up care. There is a potential risk of time commitment (missing work or school) and therefore we will be flexible and practical in scheduling convenient appointments.

- b. Steps taken to minimize the risks.

Date: July 1, 2013
Principal Investigator: [name]
Application Number: NA_00045673

All subjects will complete the exercise intervention with supervision. A licensed physical or Occupational therapist will progress the exercise intervention for each individual based on their capabilities. Subjects will be given rests whenever needed or requested.

During the walking and balance tests we will place a gait belt on all subjects and 1-2 investigators will walk behind them in case they lose their balance. We will also give a rest break when subjects feel fatigued, short of breath, or simply want a break. They will be allowed to stop any test at any time or rest between tests. In previous studies there has been no incident that would suggest any significant potential risk.

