treatment. Our comprehensive methodology and careful quantification of sensory and motor impairments and walking may be a more sensitive way to quantify subtle changes in disability, and may be more closely related to the function of the corticospinal tract. Our results, therefore, have the potential to support new clinical markers that more closely follow changes in physical function in AMN. We are also directly testing a treatment intervention that will provide scientific rationale for predicting the best responders to a progressive resistance training program. We will evaluate not only the improvement in physical function but also the extent that myelin and axon structure and integrity can predict who best responds to the intervention. Overall, the linking of clinical impairments and disabilities with anatomic MRI measures will not only be important for better defining disability in female carriers but it will also help to guide physicians and rehabilitation therapists in predicting who is likely to respond to rehabilitative interventions, as well as for optimizing the effects of future neuroprotective pharmacological interventions.

9. Payment and Remuneration

- a. Detail compensation for participants including possible total compensation, proposed bonus, and any proposed reductions or penalties for not completing the protocol.

All subjects will be compensated \$25 for participating in the laboratory sessions. Subjects will be paid in cash upon completion of the study. If subjects leave the study before it is completed, they will not receive payment.

10. Costs

- a. Detail costs of study procedure(s) or drug (s) or substance(s) to participants and identify who will pay for them.

The subjects will not be charged for any of the procedures in the study. They will only be responsible for the cost of any travel to and from the Institute as well as any meals they eat while participating. The costs of parking at the Institute's garage will be covered. All subjects will be provided \$150 for the costs of their participation in the exercise program. MRI scan fees for women carriers will be covered by a research grant from the European Leukodystrophy Association. Requests for further financial support are underway through the NBRU, and NIH mechanisms. Funding for up to four individuals is also available to help offset the financial burdens of travel costs.

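### Everyone trains, unblinded and after a single baseline test, so pre-to-post change is not an estimate of the training effect and the claims built on it need restating

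*Combined protocol and SAP*

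**What the plan says.** The comparison is by disease status: "We will test female heterozygote carriers of X-ALD and healthy age- and gender-matched controls" (Section 4a). Training is not what separates the groups. Section 4c states "All subjects in the study will take part in the exercise intervention", Section 7b adds "All subjects will complete the exercise intervention with supervision", and Section 10 gives every subject $150 towards the exercise program. Section 4e, headed "Justification for inclusion of a placebo or non-treatment group", is answered N/A. On masking, Section 4c says "We are unable to blind the subjects or testers to the intervention" and calls this a limitation.

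Testing takes place at baseline, week 12 and week 18 (Section 4a), with no second pre-training test. The training outcome is a composite of sit to stand, Up and Go, 25-foot walk and 6-minute walk (Study Statistics a).

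Study Statistics b, item 1, offered as a way to determine response to the three months of exercise, plans an unpaired t test of change between groups, and adds "Changes between pre- and post-trial within groups will also be compared with paired t tests". Item 2 sets the change from post-training to follow-up against the change from pre- to post-training.

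Primary objective 2 (Section 2) asks how far tract anatomy can "predict who will respond best to three months of progressive resistance training (PRT) in female carriers". Section 8a describes the study in stronger terms: "We are also directly testing a treatment intervention that will provide scientific rationale for predicting the best responders". Sections 1 and 8a both expect the results to help physicians and therapists predict who will respond to rehabilitation.

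**The concern.** The four tests in the composite depend on effort and on familiarity with the task. A woman who repeats them 12 weeks later, knowing that she has trained and assessed by someone who also knows, may score better for reasons unrelated to muscle strength. With no untrained group and no repeat baseline, nothing in the data shows how much of the change is of that kind.

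Two conclusions are at stake. One is that PRT improves function in carriers, which a significant paired t test would appear to show. The other is that an imaging measure predicts response to PRT, when the data can show only that it goes with change during a period in which everyone trained.

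**Working it through.** **No plan figure to reproduce.** The documents give no retest gain and no SD of change for the composite. The sample-size statement (12 subjects, one SD, power 0.8) concerns a difference between groups and does not bear on this point.

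**What each planned contrast contains.** Write a woman's change from baseline to week 12 as training effect T, plus practice and expectation P, plus regression to the mean R, plus random variation.

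- *Paired t test within carriers:* tests whether mean(T + P + R) is zero. It does not isolate T.
- *Unpaired t test, carriers against controls:* tests (T + P + R in carriers) minus (T + P + R in controls). Both groups have a T. If both gain equally from training, the difference is zero however large the gain.
- *Follow-up contrast, item 2:* a gain to week 12 followed by a plateau fits retained practice and retained training benefit equally well. A later fall fits lost training benefit, but also expectation fading once the program ends. The two intervals differ in length (12 weeks, then 18 − 12 = 6), and the plan does not say whether subjects stop training after week 12.

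**Regression to the mean.** Section 5 admits carriers on hip flexion of 6.6-15.8 kg or hip extension of at most 18.3 kg. The flexion window is the preliminary mean plus or minus one SD (11.2 − 4.6 = 6.6; 11.2 + 4.6 = 15.8). It is symmetric about that mean, so by itself it need not push the average either way. The extension limit is a one-sided cap, which favors women who test low on the day. Controls have no stated strength limits. The net size cannot be computed from the documents.

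**Size for the paired t test.** Assumptions: T = 0; practice or expectation shifts the mean by d SD of change; two-sided alpha 0.05. The sample sizes are the plan's 15 carriers, or 12 completers. The probability of significance is P(|t′| > critical value), where t′ is noncentral t with n − 1 degrees of freedom and noncentrality d√n. Critical values are 2.145 (14 df) and 2.201 (11 df).

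| Assumed d | n = 15: d√15 | Significant | n = 12: d√12 | Significant |
|---|---|---|---|---|
| 0 | 0 | 5% | 0 | 5% |
| 0.2 | 0.775 | 11.2% | 0.693 | 9.7% |
| 0.3 | 1.162 | 19.2% | 1.039 | 15.8% |
| 0.5 | 1.936 | 43.8% | 1.732 | 35.3% |

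**Objective 2.** For a baseline imaging measure X, cov(X, change) = cov(X, T) + cov(X, P) + cov(X, R) + cov(X, random variation). If P is the same for every carrier, cov(X, P) = 0 and the slope is untouched. Random variation unrelated to X also contributes zero and only lowers power and R². What remains is that P, R or natural change may vary with X, for instance if less affected women learn the tests faster. Only untrained carriers would show how large those terms are, so an observed association cannot be assigned to T.

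**The case against.** The strongest reply is that neither primary objective claims efficacy. Objective 2 concerns differences among women who all train, and predicting change in trained women needs no control group. The paired t test is listed under secondary outcomes. Its null is zero mean change, so a rejection is wrong only if it is read as a PRT effect. Section 4c admits the lack of blinding, and the strongest wording sits in an ethics-form section on benefits. A single-group study is also a reasonable choice in a rare disease.

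Much of this stands, and it limits the point to inference and wording. It does not remove it. Item 1 offers the within-group test as a measure of response to the exercise, and Section 8a says without qualification that the treatment is being tested. The limitation admitted in Section 4c is blinding only. Its stated remedy, guidelines for progressing the exercise, addresses neither test practice nor the missing comparator.

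Natural worsening could offset some practice gain. Section 3 describes progression over 5 to 20 years in a variable pattern and gives no rate on these tests, so no offset can be computed.

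A reader might infer that the 11-44% figures also describe false imaging findings under objective 2, or that visit-to-visit noise could create such findings. Neither follows: with no training effect and a uniform shift, the test of the imaging association keeps its nominal 5% error. Nor does the plan say that it will identify responders or report PRT as effective; its phrase is about a rationale for predicting the best responders.

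**Conclusion.** The concern holds as a limit on interpretation, and the wording should be changed. That everyone trains, that nobody is blinded and that there is one pre-training test are all plain in the text, and no planned analysis recovers the effect of training.

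For the within-carrier paired t test alone, assumed shifts of 0.2 to 0.5 SD of change with no PRT effect give significance 11% to 44% of the time with 15 carriers and 10% to 35% with 12. The shifts are assumptions, so the range illustrates the problem and is not an estimate for this trial.

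For objective 2 the limit is one of meaning: an association with change cannot be shown to be specific to PRT. No bias in it has been demonstrated. Objective 1, which relates imaging to impairment without reference to training, is unaffected.

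**What to change.** - In Section 2, restate objective 2 as the association of baseline tract measures with 12-week change among women who all trained. Baseline is the only visit at which Section 4a schedules MRI. Align the matching claims in Sections 1 and 8a.
- In Study Statistics b, state that within-group change includes practice, expectation and possible regression to the mean and is not an estimate of the PRT effect, and that the carrier-control and follow-up contrasts do not isolate that effect either.
- In Section 8a, remove the statement that the treatment is being directly tested.

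The cost is wording and a more modest claim; no visit, arm or measurement changes.

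Leaving the healthy controls untrained is not recommended as a remedy. It would confound training with disease status, leave expectation and selection on strength uncontrolled, and do nothing for the imaging question. A claim about response to PRT itself would need untrained carriers.
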